4.7.5 Subject replacement

The total number of subjects proposed for this clinical investigation is up to 10. If a subject withdraws pre-operatively, they will be replaced by a newly recruited subject who meets the selection criteria for participation.

4.7.6 Point of enrollment

Subjects are recruited to the study by the investigators usually during the course of medical consultation. Subjects will be sequentially enrolled once Cochlear Americas receives a properly executed Informed Consent form and has approved the preoperative candidacy evaluation.

4.7.7 Total expected duration of the clinical investigation

The total expected duration of the clinical investigation is 18 months. The total duration will be dependent on the ability to recruit the required number of subjects within the enrollment period.

5 JUSTIFICATION FOR THE DESIGN OF THE CLINICAL INVESTIGATION

A multi-center clinical early feasibility trial was performed with 17 cases being implanted with version 1 of the electrode array/sheath assembly (3). Electrode tip fold-over was identified in 32% of cases and due to this complication, 23% of cases received a commercial back-up device (CI24RE(CA) or CI512). Complications were related to device deficiencies and surgical protocol deviations. Hearing preservation was generally poor and most subjects lost their residual

⁴ Withdrawal of consent is defined as the subject's voluntary decision to revoke consent to continue participation in the study.

⁵ Subject withdrawal from the study is defined as an Investigator decision. The Investigator may elect to withdraw a subject from the study at any time if he/she considers that remaining in the study compromises the patient's health or if the Investigator considers the subject lost to follow-up.

hearing in the implanted ear. The participants recruited for the early feasibility trial met current local indications for a conventional implant. The inclusion criteria specified an unaided hearing threshold in the ear to be implanted of equal to or better than 80 dB HL at 500Hz. Speech perception in quiet and noise significantly improved pre-operatively-to-post-operatively. Follow-up of these cases is now more than 5 years with no device related adverse events reported – all devices remain functional and in place.

Rotation of the electrode in the sheath may have contributed to the adverse device effects seen in the early feasibility trial and lead to further sheath design by Cochlear Limited. Most of the development focussed on the sheath until version 4 where the sheath to guide-tube assembly was reconfigured to further improve handling and visibility. In the intermediate designs tip folding occurrence was reduced by removing rotation and finally by modification of the slit in the sheath. The slit allows the sheath to be removed after the electrode is fully deployed. The final version improved the stability of the sheath especially when some bending of the array and sheath occurs.

Pre-clinical testing with the CI532 was performed with four versions of the electrode-sheath assembly over four rounds of formal temporal bone trials. The temporal bone data on the EA32 (using the latest sheath design) shows perimodiolar positioning in a large majority of cases with a relatively low potential for intra-cochlear trauma shown by a dislocation rate of 3.3%. Once use errors were taken into account the tip fold-over rate was 3/110 or <3%.

Currently, an outside the United States (OUS) multicenter clinical investigation is being undertaken to determine if a low rate of dislocation can be achieved in clinical cases. Fourteen adult candidates have been successfully implanted with the CI532 device (Melbourne, Australia and Las Palmas, Spain) at the time of this submission with no scala dislocation or electrode tip fold-over. Due to early success in the positioning of the CI532 device, further clinical evaluation is warranted to assess the feasibility of accessing acoustic hearing postoperatively in a clinical population with greater potential to preserve residual hearing.

The primary objectives of the clinical investigation is to 1) evaluate preoperative to 6 months post-activation performance outcomes in the best unilateral listening condition using AzBio Sentences in speech-weighted noise (SWN) and 2) report the medical/surgical and device related adverse events compared to the current approved labelling with regard to type, frequency and seriousness at 6 months post-activation. In order to demonstrate the atraumatic nature of the CI532 electrode design and insertion technique, as well as the possibility of fitting of the acoustic component postoperatively, the inclusion criteria has been structured to capture subjects who currently meet the clinical criteria for cochlear implantation but who also possess unaided audiometric thresholds between 40 and 65 dB HL in the low frequencies. The secondary objectives of this clinical investigation are to evaluate Patient Reported Outcomes (PRO) preoperatively to 6 months postactivation for the Speech Spatial and Quality of Hearing scale (SSQ) and the Glasgow Benefit Inventory (GBI) at 6 months postactivation. The outcomes from this feasibility study may be used to support the development of a randomized multicenter

clinical investigation evaluating the functional hearing preservation with the CI532 cochlear implant.

6 CLAIMS AND INTENDED PERFORMANCE

The claims and intended performance of the study device that are to be verified are:

1. The number and percentage of subjects who were able to be fit with the acoustic component postoperatively.
2. Pre-to-post performance benefits with the CI532 cochlear implant for speech recognition in the best unilateral listening condition.

7 PROCEDURES

7.1 Medical history and Counseling

Information regarding subject hearing-history (e.g., etiology, onset of hearing loss, duration of severe-to-profound hearing loss, amplification use) will be obtained and reported on the respective case-report form. In addition, patients will be carefully and extensively counseled to ensure that their expectations from cochlear implantation are reasonable and appropriate (as determined by the Investigator).

7.2 Audiogram (Candidacy, Activation, 3, 6 and 12 months post-activation)

An unaided audiogram will be performed for both ears at Candidacy⁶, Initial Activation, 3, 6 and 12 months post-activation at the following pure-tone frequencies:

- Air Conduction: 125, 250, 500, 750, 1000, 2000, 3000, 4000, 6000 & 8000 Hz

Air conduction thresholds >80 dB HL at 125 Hz, >90 dB HL at 250 Hz, >100 dB at 8000Hz and >120 dB for other test frequencies will be marked NR (no response). Thresholds that exceed the air conduction limits of the audiometer, where the recipient reports feeling the acoustic stimuli, shall be recorded as vibrotactile (VT).

- Bone conduction: 125⁷, 250, 500, 750, 1000, 2000, 3000, 4000 Hz

Bone conduction thresholds >20 dB HL at 125 Hz, >30 dB HL at 250 Hz, >60 dB HL at 500 Hz and >70 dB HL for other test frequencies will be marked NR (no response).

⁶ If it is more than 90 days past the date of the Candidacy Evaluation, candidacy needs to be reconfirmed by repeating audiometric threshold test measures. Any changes observed will need to be reviewed in consultation with the Sponsor prior to surgery occurring.

⁷ Bone conduction measures at 125 Hz are optional based on potential audiometric equipment limitations.

An aided audiogram will be performed for both ears at candidacy, and the implanted ear at initial activation⁸, three, six and 12 months post-activation at the following frequencies using warble tones:

- Aided thresholds: 125, 250, 500, 750, 1000, 2000, 3000, 4000 Hz

7.3 Speech recognition (Candidacy, 3, 6 and 12 months post-activation)

Speech recognition will be measured pre-operatively, and at 3, 6, and 12 months post activation. Pre-operatively, speech recognition will be evaluated in the unilateral aided condition with the contralateral ear masked or plugged. Post-activation, the best unilateral listening condition will be evaluated; “Implant ear” using the acoustic component and/or the CI SP alone on one ear with the contra-lateral ear plugged or masked. If the subject uses the acoustic component, speech perception will also be completed as electric alone. Post-activation speech recognition will be evaluated with default input processing options.

Assessment of speech perception in quiet will be measured using two lists of CNC monosyllabic word test (7) at 60 dBA in the S0 speaker orientation (Figure 2).

Assessment of speech understanding in noise will be measured using a list of 20 sentences drawn from the AzBio sentences lists (8) at 60 dBA at a fixed +5 dB signal-to-noise ratio (SNR) in the S0N90 or S0N270 speaker orientation (Figure 2). The competing noise will be speech weighted noise (SWN).

Test lists will be randomized throughout the clinical investigation in order to avoid learning effects.

Performance benefits are change in scores pre- to post-operatively:

1. Gain in speech recognition in quiet (% correct)
2. Gain in speech recognition in noise (% correct)

7.4 Speech, Spatial, Qualities of Hearing Scale – SSQ (Candidacy & 6 months post-activation)

Subjective quality assessment will be measured using the SSQ preoperatively and again at 6 months post-activation.

Performance benefits are a change in scores pre- to post-operatively:

1. Gain in SSQ score (-10 to +10)

⁸ Assessing aided thresholds after the initial activation will only be conducted if there is a shift in unaided hearing of more than 10 dB HL (for the better or worse) at two or more audible frequencies.

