4 DESIGN OF THE CLINICAL INVESTIGATION

4.1 General

The Implantation of the Cochlear™ Nucleus® CI532 in Adults feasibility study will be conducted as a single-site, prospective, single-arm clinical study, evaluating the safety and functionality of the Cochlear Nucleus CI532 cochlear implant in up to 10 subjects who meet current cochlear implant indications with low frequency unaided thresholds at 250 and 500 Hz between 40 and 65 dB HL. A single-subject repeated-measures analysis will be employed whereby subjects will act as their own control. A single-subject research design is appropriate since it accommodates the heterogeneity that characterizes hearing-impaired populations. Blinding procedures are not appropriate for this trial design, as it is not possible to conceal the presence, or absence, of a cochlear implant from device recipients and/or clinical investigators.

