4.3 Endpoints

4.3.1 Primary endpoints

The six month post-activation visit serves as the primary endpoint for data collection related to:

1. Efficacy – To evaluate preoperative to 6 months post-activation performance outcomes in the best unilateral listening condition using AzBio Sentences in speech weighted noise (SWN).
2. Safety – Report of medical/surgical and device related adverse events compared to the current approved labelling with regard to type, frequency and seriousness at 6 months post-activation.

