10.1 Efficacy Measurements

At a minimum, individual data will be tabulated and summarized for all measures to establish the proportions of those subjects showing improvement, no change, and decrement in performance.

The efficacy objectives include:

- a) To understand if subjects implanted with the CI532 can retain low frequency thresholds and be fit with the acoustic component

Audiometric data will be collected and acoustic fittings will be tracked at each follow up time point. For those fit with the acoustic component, outcomes will be assessed with and without the acoustic component.

- b) To understand if implantation with the CI532 results in improved postoperative speech perception outcomes in both quiet and noise when using the best unilateral listening condition

Device efficacy will be evaluated by comparisons of group and individual performance pre- and postoperatively at 3, 6, and 12-months post-activation. Performance benefits are change in scores pre- to post-operatively:

- Gain in speech recognition in quiet on CNC words (% correct)
- Gain in speech recognition in noise on AzBio Sentences (% correct)

c) To understand if implantation with the CI532 results in improved patient reported hearing performance and health utility

Scores from the SSQ obtained postoperatively will be compared with those obtained preoperatively, prior to implantation. The SSQ will act to provide a measure of hearing performance as perceived by the subjects. The GBI will provide a measure of change in health status as a result of cochlear implantation. Since the GBI is structured as a post-intervention (change) metric, there will be no preoperative measures derived for comparison with postoperative scores.

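### Protocol 7.3: randomising test lists balances list difficulty but cannot keep task practice out of the pre-operative to 6-month AzBio gain

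*Protocol*

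**What the plan says.** Section 7.3 fixes the order of testing: "Speech recognition will be measured pre-operatively, and at 3, 6, and 12 months post activation". Speech in noise is scored at each test "using a list of 20 sentences drawn from the AzBio sentences lists", at a fixed signal-to-noise ratio. A second post-activation condition is added for some subjects: "If the subject uses the acoustic component, speech perception will also be completed as electric alone". The one measure against learning is the sentence "Test lists will be randomized throughout the clinical investigation in order to avoid learning effects".

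The same section defines the outcome as a raw difference: "Performance benefits are change in scores pre- to post-operatively". Section 4.3.1 makes the AzBio-in-noise change from pre-operative to 6 months the primary efficacy endpoint. The trial has a single arm, and section 4.1 says: "A single-subject repeated-measures analysis will be employed whereby subjects will act as their own control". Section 10.1(a) plans to assess outcomes with and without the acoustic component in those fitted with it.

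The protocol does not give the number of lists in either bank, does not say whether lists are drawn with or without replacement, and describes no practice list or repeated baseline.

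**The concern.** The stated means does not achieve the stated purpose. Learning has two parts here. One is memory of particular sentences, which a suitable list schedule can prevent. The other is practice with the task itself: listening for sentences in noise, guessing from context, and knowing the procedure. Which list is used has no bearing on the second part. The pre-operative test always comes first and no concurrent group is tested on the same calendar, so practice can only push the change score in one direction, and nothing in the design separates it from the effect of the implant.

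The change score carries weight in the protocol. Section 6 lists pre-to-post benefit among the claims to be verified. Section 10.1 sorts individuals into improved, unchanged and worse. Section 5 says the results may support a later randomised trial. An upward shift would move borderline subjects towards improvement and would pass into the planning of that trial.

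**Working it through.** The protocol states no learning effect and no list-bank size, so there is no figure of its own to reproduce. The check has three parts.

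**1. What list randomisation does to the mean change.** Write a score as the sum of true ability, a practice term for the testing occasion, a list-difficulty term and error. The change from pre-operative (occasion 1) to 6 months (occasion 3) is then

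D = g + (p3 − p1) + (l6 − l0) + error,

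where g is the true gain, p is practice and l is list difficulty. Random assignment of lists gives E(l6 − l0) = 0. It leaves p3 − p1 untouched, so E(D) = g + (p3 − p1).

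As an illustration with assumed values, suppose practice is worth c points per occasion and g = 0. Then E(D) = 2c. A simulation with randomly assigned lists gave mean changes of 0.0, 2.0, 4.0 and 10.1 points for c = 0, 1, 2 and 5. The simulation shows only that the list term averages out while the occasion term stays. It says nothing about how large c is.

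**2. List reuse.** Administrations per subject under section 7.3:

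- AzBio, one list per test: 1 + 3 = 4, or 1 + 3 × 2 = 7 for a subject tested in two conditions at every post-activation visit.
- CNC, two lists per test: 2 + 3 × 2 = 8, or 2 + 3 × 4 = 14.

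Before the 6-month visit a subject has heard k = 2 AzBio lists (pre-operative and 3 months), or k = 3 with an electric-alone test at 3 months. With independent draws from an assumed bank of L lists, the chance that the 6-month list was heard at an earlier visit is 1 − (1 − 1/L)^k:

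| Assumed L | k = 2 | k = 3 |
|---|---|---|
| 8 | 1 − (7/8)² = 23% | 1 − (7/8)³ = 33% |
| 15 | 1 − (14/15)² = 13% | 1 − (14/15)³ = 19% |
| 33 | 1 − (32/33)² = 6% | 1 − (32/33)³ = 9% |

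Without replacement every entry is 0%.

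**3. Order of conditions.** Section 7.3 randomises lists but states no order for the best-condition and electric-alone tests within a visit. Section 10.1(a) compares the two. If one order were used throughout, practice within the visit would be mixed into that comparison. If electric-alone always came second, practice would favour it and understate the acoustic benefit; the reverse order would overstate it.

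**The case against.** The strongest objection is that this is a generic limit of every single-arm pre/post study, openly chosen and justified in section 4.1. The study has up to 10 subjects, no formal hypothesis (section 2.2) and no pass/fail criteria (section 10), so no decision rule can go wrong. That stands, and it sets the severity. The mention in section 10.4 of a p-value for primary hypothesis tests does not change it. The objection does not rescue the sentence in section 7.3, which claims that randomisation deals with learning.

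A second objection is that the scored baseline may not be the subject's first exposure. Criterion 1b in section 4.7.1 requires aided open-set sentence scores for the ear to be implanted and for the best-aided condition, so subjects have done sentence testing in order to qualify. This may absorb some early practice. The protocol does not name that test, say whether it is given in noise, or place it before the scored baseline, so the point stands only in part.

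A reader might infer three stronger things that the documents do not support:

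- *That lists do recur.* Section 7.3 neither allows nor excludes reuse. Given its stated purpose, a shuffled order of different lists is a natural reading, and a schedule may sit in a test manual that is not shown.
- *That electric-alone always comes second.* The sentence adds a condition; it does not fix a sequence.
- *That a definite share of the gain is practice.* The documents give neither a practice effect nor the mean and SD of the change, so any such percentage would rest on assumed numbers. They also contain no evidence that practice persists across tests months apart.

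**Conclusion.** The point holds in a limited form and is minor. Randomising lists balances their difficulty; it does not remove task practice from a change score whose first test always precedes the second and which has no control. This follows from the design and needs no assumed figure. If practice is present, its whole expected effect is counted as gain in the primary AzBio endpoint. Its size cannot be obtained from the documents and could be close to zero.

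List reuse and condition order are gaps in the text, not demonstrated faults. The 6% to 33% range for a 6-month list heard at an earlier visit rests on independent draws and assumed banks of 8 to 33 lists, and falls to 0% if lists are not repeated. The consequence is a possible upward bias in a descriptive estimate. A baseline taken without prior practice cannot be redone after surgery, which is why the change is worth making in the protocol.

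**What to change.** In section 7.3:

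1. Assign lists to each subject from a randomised schedule drawn up in advance, without replacement. At minimum, no AzBio list heard earlier should be used for the 6-month primary test. A subject tested in two conditions throughout would need 7 scored AzBio lists plus 1 practice list, 8 in all. If the CNC bank has fewer than 14 lists, some CNC repeats are unavoidable and should be planned.
2. Give one unscored AzBio-in-noise practice list before the scored pre-operative list.
3. Alternate the order of the acoustic-plus-electric and electric-alone conditions across subjects, and record the order used.
4. Reword the sentence to say that randomisation balances list difficulty, and name residual practice as a limitation of the pre/post gain.

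The cost is a few minutes at candidacy for each of up to 10 subjects and a pre-printed schedule. The reported gain may be slightly smaller. Alternation has one side effect: in subjects tested electric-alone first, the primary 6-month test follows another list at the same visit. The schedule must therefore exclude that list too, and the recorded order allows the effect to be examined.

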7.5 Glasgow Benefit Inventory – GBI (6 months post-activation)

Health Utility assessment will be measured using the GBI at six months post-operatively.

Performance benefits are a change in scores pre- to post-operatively:

1. GBI score (-100 to +100)

7.6 Surgical Questionnaire – Intraoperatively

Surgical questionnaire will be completed by the implanting surgeon for each subject implanted.

7.7 Video (Surgery)

Surgery may be recorded via a video camera connected to the surgeon's microscope.

7.8 Imaging: X-ray (Surgery)

The presence of tip fold-over may be detected intra-operatively via planar X-ray, so that it may be corrected in-situ. Consistent with the Nucleus® CI532 cochlear implant with Slim Modiolar electrode Physician's Guide on page 81, an X-ray will be obtained prior to closure (preferably a lateral or modified Stenvers view) to confirm proper electrode placement.

7.9 Activation (approximately 1 month post-surgery)

The CI532 cochlear implant will be activated with a commercially available Nucleus CP910 or CP920 Sound Processor and Custom Sound programming software. This will take place approximately 1 month after surgery (plus/minus 2 weeks).

Impedances and T/C levels will be collected during the visit. These data will be extracted from anonymized computer record files ("CDX") produced by the Custom Sound software.

Initially the default ACE sound coding strategy will be used with the parameters pulse rate 900 pps per channel, 25 μ s / phase, mode MP1+2, and 8 maxima. These parameters may be adjusted afterward according to local procedures to improve subjective sound quality, if deemed necessary by the clinician. The sound processor should be loaded with the currently available, default input processing options.

7.10 Device characteristics (Activation and 6 months post-activation)

Device characteristics will be recorded at every post-activation visit and maintained within the subjects anonymous .cdx file.

7.11 Safety

The investigator will complete an Adverse Event (AE) and or Adverse Device Effect Case Report Form (AE and ADE CRF) if any AE or ADE is reported or observed for a subject during the investigation, even if they were acknowledged as risk factors in the Informed Consent Form.

7.12 Medical care post-investigation

Routine medical care from the implanting center will be provided for the subjects during, as well as, after the clinical investigation has been completed. Subjects will be followed-up as per the centers standard clinical procedures.

Upon completion of the study, the clinical monitor will conduct a study close-out of the investigational site. The objectives of this visit are to ascertain that all subjects are accounted for, that the regulatory records and reports are complete, verify that study device and other supplies have been accounted for and ensure that the Investigator is aware of his/her responsibilities post-study.

